14.6 Appendix 6. National Kidney Foundation Guidelines for Chronic Kidney Disease

Stages of Chronic kidney disease (National Kidney Foundation 2002):

- Stage 1- Kidney damage with normal or elevated GFR (≥ 90)
- Stage 2- Kidney damage with mild reduction in GFR (60-89)
- Stage 3- Kidney damage with moderate reduction in GFR (30-59)
- Stage 4- Kidney damage with severe reduction in GFR (15-29)
- Stage 5- Kidney failure (<15 or dialysis)

14.6.1 Estimation of GFR:

Estimates of GFR are the best overall indices of the level of kidney function. The level of GFR should be estimated from prediction equations that take into account the serum creatinine concentration and some or all of the following variables: age, gender, race, and body size. Among adults, the CKD-EPI equation provides a clinically useful estimate of GFR (Levey et al., 2009). This equation provides estimate of GFR standardized for body surface area.

14.6.2 CKD-EPI Equation:

The CKD-EPI equation performed better than the MDRD (Modification of Diet in Renal Disease Study) equation, especially at higher GFR, with less bias and greater accuracy. When looking at NHANES (National Health and Nutrition Examination Survey) data, the median estimated GFR was 94.5 mL/min per 1.73 m² vs. 85.0 mL/min per 1.73 m², and the prevalence of chronic kidney disease was 11.5% versus 13.1%. The CKD-EPI equation, expressed as a single equation, is:

$$\text{GFR} = 141 * \min(\text{Scr}/\kappa, 1)^\alpha * \max(\text{Scr}/\kappa, 1)^{-1.209} * 0.993^{\text{Age}} * 1.018 [\text{if female}] * 1.159 [\text{if black/African american}]$$

Where Scr is serum creatinine (mg/dL), κ is 0.7 for females and 0.9 for males, α is -0.329 for females and -0.411 for males, min indicates the minimum of Scr/ κ or 1, and max indicates the maximum of Scr/ κ or 1.

14.7 Appendix 7. Brief Pain Inventory- BPI (Short Form)

(www.mdanderson.org/education-and-research/symptom-assessment-tools/BPI User Guide pdf)

STUDY ID# _____ HOSPITAL # _____

DO NOT WRITE ABOVE THIS LINE

Brief Pain Inventory (Short Form)

[figure not shown]
Date: ____/____/____ Time: _____

Name: _____
Last First Middle Initial

1. Throughout our lives, most of us have had pain from time to time (such as minor headaches, sprains, and toothaches). Have you had pain other than these every-day kinds of pain today?

1. Yes 2. No

2. On the diagram, shade in the areas where you feel pain. Put an X on the area that hurts the most.

3. Please rate your pain by circling the one number that best describes your pain at its worst in the last 24 hours.

0 1 2 3 4 5 6 7 8 9 10
No Pain Pain as bad as you can imagine

4. Please rate your pain by circling the one number that best describes your pain at its least in the last 24 hours.

0 1 2 3 4 5 6 7 8 9 10
No Pain Pain as bad as you can imagine

5. Please rate your pain by circling the one number that best describes your pain on the average.

0 1 2 3 4 5 6 7 8 9 10
No Pain Pain as bad as you can imagine

6. Please rate your pain by circling the one number that tells how much pain you have right now.

0 1 2 3 4 5 6 7 8 9 10
No Pain Pain as bad as you can imagine

7. What treatments or medications are you receiving for your pain?

8. In the last 24 hours, how much relief have pain treatments or medications provided? Please circle the one percentage that most shows how much relief you have received.

0%	10%	20%	30%	40%	50%	60%	70%	80%	90%	100%
No Relief										Complete Relief

9. Circle the one number that describes how, during the past 24 hours, pain has interfered with you:

A. General Activity

0	1	2	3	4	5	6	7	8	9	10
Does not Interfere										Completely Interferes

B. Mood

0	1	2	3	4	5	6	7	8	9	10
Does not Interfere										Completely Interferes

C. Walking Ability

0	1	2	3	4	5	6	7	8	9	10
Does not Interfere										Completely Interferes

D. Normal Work (includes both work outside the home and housework)

0	1	2	3	4	5	6	7	8	9	10
Does not Interfere										Completely Interferes

E. Relations with other people

0	1	2	3	4	5	6	7	8	9	10
Does not Interfere										Completely Interferes

F. Sleep

0	1	2	3	4	5	6	7	8	9	10
Does not Interfere										Completely Interferes

G. Enjoyment of life

0	1	2	3	4	5	6	7	8	9	10
Does not Interfere										Completely Interferes

Copyright 1991 [name]
 Pain Research Group
 All rights reserved.

14.8 Appendix 8. Premedication Discontinuation Guide

Patients on agalsidase alfa can be included in the study when under premedication to diminish the side effects to the drug.

During the first 2 months of PRX-102 treatment (5 infusions), the Investigator will manage a stepwise discontinuation of the premedication based on the appropriate tolerability of the patient to the changes. Premedication will resume in the case that the patient will present signs and symptoms of non-tolerability of the infusion.

All cases of non-tolerability and need of premedication will be discussed between the Investigator and the Medical Director before reaching infusion 7 and evaluating the reduction of infusion rate, see also Appendix 2.

14.9 Appendix 9. EQ-5D-5L

Figure 1: EQ-5D-5L (UK English sample version)

Under each heading, please tick the **ONE** box that best describes your health **TODAY**

MOBILITY

- I have no problems in walking about
- I have slight problems in walking about
- I have moderate problems in walking about
- I have severe problems in walking about
- I am unable to walk about

SELF-CARE

- I have no problems washing or dressing myself
- I have slight problems washing or dressing myself
- I have moderate problems washing or dressing myself
- I have severe problems washing or dressing myself
- I am unable to wash or dress myself

USUAL ACTIVITIES (e.g. work, study, housework, family or leisure activities)

- I have no problems doing my usual activities
- I have slight problems doing my usual activities
- I have moderate problems doing my usual activities
- I have severe problems doing my usual activities
- I am unable to do my usual activities

PAIN / DISCOMFORT

- I have no pain or discomfort
- I have slight pain or discomfort
- I have moderate pain or discomfort
- I have severe pain or discomfort
- I have extreme pain or discomfort

[figure not shown]
ANXIETY / DEPRESSION

- I am not anxious or depressed
- I am slightly anxious or depressed
- I am moderately anxious or depressed
- I am severely anxious or depressed
- I am extremely anxious or depressed

- We would like to know how good or bad your health is **TODAY**.
- This scale is numbered from **0** to **100**.
- **100** means the best health you can imagine.
0 means the worst health you can imagine.
- Mark an **X** on the scale to indicate how your health is **TODAY**.
- Now, please write the number you marked on the scale in the box below.

YOUR HEALTH TODAY =

The best health
you can imagine

The worst health
you can imagine

1. ABBREVIATIONS

AE	Adverse Event
ACEi	Angiotensin-Converting Enzyme Inhibitor
ADA	Anti-Drug Antibodies
ARB	Angiotensin Receptor Blocker
BLA	Biologics License Application
BPI	Brief Pain Inventory
CKD	Chronic Kidney Disease
CRF	Case Report Form
CSR	Clinical Study Report
ECG	Electrocardiography
EDC	Electronic Data Capture
eGFR	Estimated Glomerular Filtration Rate
EP	Efficacy Population
FCE	Fabry Clinical Events
FD	Fabry Disease
Gb3	Globotriaosylceramide
HBsAg	Hepatitis B Surface Antigen
HCV	Hepatitis C Virus
HIV	Human Immunodeficiency Virus
IRR	Infusion Related Reaction
IV	Intravenous
IRR	Infusion Related Reactions
KD	Kidney Disease
LVH	Left Ventricular Hypertrophy
LVM	Left Ventricular Mass
LVMi	Left Ventricular Mass Index
Lyso-Gb3	Globotriaosylsphingosine
MedDRA	Medical Dictionary for Regulatory Activities
MRI	Magnetic Resonance Imaging
MSSI	Mainz Severity Score Index
NTF	Note to File
NSR	Normal Sinus Rhythm
PPEP	Per Protocol Efficacy Population
PT	Preferred Term
PrT	Prothrombin Time

PTT	Partial Thromboplastin Time
SAE	Serious Adverse Event
SAP	Statistical Analysis Plan
SDTM	Study Data Tabulation Model
SOC	System Organ Class
SP	Safety Population
TEAE	Treatment-emergent adverse event
UPCR	Urine Protein to Creatinine Ratio
WHO	World Health Organization

2. INTRODUCTION

The statistical analysis plan (SAP) contains the analysis information in detail on the definition of the analysis populations, derivation of variables, convention of analysis scope, and statistical methodology for the analyses of safety and efficacy parameters of pegunigalsidase alfa (formerly known as PRX-102) administered by intravenous infusion based on the data collected per the protocol PB-102-F30, a phase 3 study sponsored by Protalix, Ltd. In case of disagreement between the SAP and the Clinical Study Protocol, the SAP prevails.

Any deviations from this SAP during the actual data analysis will be documented properly in a change request or a note-to-file document, as well as in the final Clinical Study Report (CSR).

3. OBJECTIVES AND ENDPOINTS

3.1. Objectives

The primary objective of this trial is to evaluate the safety of pegunigalsidase alfa in patients with Fabry disease currently treated with agalsidase alfa (Replagal®).

The secondary objective of this trial is to evaluate the efficacy of pegunigalsidase alfa in patients with Fabry disease currently treated with agalsidase alfa (Replagal®).

3.2. Endpoints

3.2.1. Safety Endpoints

- Change from baseline in:
 - Clinical laboratory tests
 - Physical examination
 - Electrocardiogram
- Treatment-emergent adverse events
- Assessment of the injection site and infusion-related reactions (IRR), as part of the adverse events
- Ability to taper off infusion premedication after switch to pegunigalsidase alfa
- Requirement for use of premedication overall to manage infusion reactions
- Treatment-emergent anti-pegunigalsidase alfa antibodies

3.2.2. Efficacy Endpoints

- Change in estimated glomerular filtration rate (eGFR_{CKD-EPI})
- Left Ventricular Mass Index (g/m²) by MRI
- Plasma Globotriaosylsphingosine (Lyso-Gb3)
- Plasma Globotriaosylceramide (Gb3)
- Urine Globotriaosylsphingosine (Lyso-Gb3)
- Protein to creatinine ratio (UPCR) spot urine test
- Frequency of pain medication use
- Exercise tolerance (Stress Test)
- Short Form Brief Pain Inventory (BPI)
- Mainz Severity Score Index (MSSI)
- Quality of life EQ-5D-5L
- Fabry Clinical Events (FCE)

4. STUDY DESIGN

This is an open label switch over study to assess the safety and efficacy of pegunigalsidase alfa in patients treated with agalsidase alfa (Replagal[®]) for at least 2 years and on a stable dose (>80% labelled dose/kg) for at least the last 6 months. Patients will be screened and evaluated over 3 months while continuing on agalsidase alfa. Following the screening period, patients will be enrolled and switched from their agalsidase alfa treatment to receive intravenous (IV) infusions of pegunigalsidase alfa 1 mg/kg every two weeks for 12 months. No more than 25% of treated patients will be female.

At the time of enrollment, premedication, if used for the agalsidase alfa infusions before enrollment, will be continued through the first infusion with pegunigalsidase alfa and then gradually tapered at the Investigator's discretion during the first 2 months of treatment. The first infusions of pegunigalsidase alfa will be administered under controlled conditions at the investigation site. The patient can receive pegunigalsidase alfa infusions in a home care setting once the Investigator and Sponsor Medical Director agree that it is safe to do so.

4.1. Sample Size and Statistical Power Consideration

No formal sample size calculation has been performed for this study.

The sample size of 22 patients is adequate to evaluate the safety of switching from agalsidase alfa to pegunigalsidase alfa in this orphan disease in which patient recruitment in clinical trials is difficult.

4.2. Study Flow Chart:

Activity	Screening Period		Visits Treatment Period Pegunigalsidase alfa						
	Screening Visit (-3 Month)	Visit A (-2 Month) and B (-1 Month)	Visit 1	Visits 2, 4, 6, 8, 10, 12, 13, 15, 17, 19, 21, 23, 25, 26	Visits 3, 5, 9, 11	Visits 7, 20 (Months 3 and 9)	Visit 14 (Month 6)	Visits 16, 18, 22, 24	Visit 27 (Month 12)
Sign IC	x								
Assign screening number	x								
Medical history	x								
Demographics	x								
Alpha-galactosidase activity in plasma and leucocytes	x								
Historical serum creatinine	x								
Vital signs (blood pressure, pulse, temperature and respiration)	x		x	x	x	x	x	x	x
Body weight	x		x			x	x		x
Body height	x								
Physical examination	x		x			x	x		x
Concomitant medications (including pain and premedications)	x	x	x	x	x	x	x	x	x
Hematology	x		x			x	x		x
Biochemistry	x		x			x	x		x
Serum Creatinine and Cystatin C	x	x	x		x	x	x	x	x
Urinalysis – dipstick	x		x			x	x		x
Protein/Creatinine ratio spot urine test	x	x	x			x	x		x
HbsAg, HCV & HIV	x								
Serum pregnancy test (beta HCG)	x		x						
Urine Lyso Gb3 concentration	x		x			x	x		x
Plasma Lyso Gb3	x		x			x	x		x
Plasma Gb3	x		x			x	x		x

Activity	Screening Period		Visits Treatment Period Pegunigalsidase alfa						
	Screening Visit (-3 Month)	Visit A (-2 Month) and B (-1 Month)	Visit 1	Visits 2, 4, 6, 8, 10, 12, 13, 15, 17, 19, 21, 23, 25, 26	Visits 3, 5, 9, 11	Visits 7, 20 (Months 3 and 9)	Visit 14 (Month 6)	Visits 16, 18, 22, 24	Visit 27 (Month 12)
Anti-pegunigalsidase alfa Antibodies (IgG)			x		x	x	x		x
Electrocardiography (ECG)	x		x			x	x		x
Chest X-ray	x								
Cardiac function assessment (echocardiography and stress test)	x		x				x		x
Cardiac MRI			x				x		x
Inclusion/exclusion criteria	x								
Request for subject approval	x								
Enrollment approval		x ¹							
Mutation analysis			X						
PrT, PTT	X								
C3, C4	x								
Vit D	x								
Short Form Brief Pain Inventory (BPI)			x			x	x		x
Brain MRI			x						x
Mainz Severity Score Index (MSSI)			x				x		x
EQ-ED-5L			x				x		x
Pegunigalsidase alfa infusion + clinical observation			x	x	x	x	x	x	x
Adverse event assessments		x	x	x	x	x	x	x	x

1 After Visit B

5. ANALYSIS POPULATION

5.1. Safety Population

The safety population (SP) consists of all subjects who received any dose of pegunigalsidase alfa in the study. All safety analyses will be based on this population.

5.2. Efficacy Population

The efficacy population (EP) consists of all subjects who have at least one visit with an efficacy evaluation after the first pegunigalsidase alfa infusion. All efficacy analyses will be based on this population.

5.3. Per Protocol Efficacy Population

The per protocol efficacy population (PPEP) consists of all subjects who completed the 12-month treatment period with efficacy data available and with no major protocol violations. The major protocol violations will be confirmed at the clean file meeting and prior to database lock of the final analysis. All efficacy analyses will be performed on this population as well for sensitivity purposes. In case that the Per Protocol and the Efficacy population are identical then the Per Protocol output will not be generated.

6. TREATMENT DESCRIPTIONS

Unless otherwise indicated, on the summary tables, the treatment will be identified by pegunigalsidase alfa, where applicable.

7. STATISTICAL ANALYSIS METHODS AND ISSUES

7.1. Statistical Methods

Descriptive statistics, namely sample size (n), mean and its standard error, standard deviation, median, minimum and maximum for continuous variables, and count and percentage for categorical variables, will be provided.

Statistical comparison of the efficacy endpoints, the estimated slopes of eGFR, between pre and post treatment of pegunigalsidase alfa will be performed using parametric and/or non-parametric approaches and are to be described in detail in Section 10 of this document.

7.2. Missing Data

Incomplete dates of start treatment of Fabry disease, will be imputed as follows:

- The middle of month (i.e. 15) will be imputed, if only day is missing,
- The middle of year (i.e. July 1) will be imputed if both month and day are missing.
- No imputation will be done in case the year is missing.

Imputations of missing data associated with adverse events (AE) will be specified in Section 9.1.

No other imputation will be made for missing values of safety or efficacy endpoints.

7.3. Baseline Definition

The baseline for this study is defined as the assessment made at Visit 1 prior to the first infusion of pegunigalsidase alfa. If not available, the last assessment before receiving the first treatment of pegunigalsidase alfa will be used as baseline.

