6. INVESTIGATIONAL PLAN

6.1 Overall Study Design and Plan – Description

This is an open label switch over study to assess the safety and efficacy of PRX-102. Patients treated with agalsidase alfa for at least 2 years and on a stable dose (>80% labelled dose/kg/) for at least 6 months. Patients will enter the study for 3 month Screening period for baseline data generation. Eligible patients will be switched from their agalsidase alfa treatment to receive intravenous (IV) infusions of PRX-102 1 mg/kg every two weeks for 12 months. No more than 25% of treated patients will be female.

At the time of enrolment, premedication, if used for the agalsidase alfa infusions before study entry, will be continued during the Screening period and to the first infusion with PRX-102 treatment and then gradually tapered at the investigator's discretion during the first 2 months. The first infusions of PRX-102 will be administered under controlled conditions at the investigation site. The patient can receive their PRX-102 infusions at a home care setup once the investigator and Sponsor Medical Director agree that it is safe to do so.

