9.1 Study Visits

9.1.1 Screening Visit S1 (3 Months \pm 7days before Visit 1)

The following procedures will be performed:

- Administration of informed consent
- Assign Screening number
- Medical history, including Fabry disease history
- Demographics
- Alpha-galactosidase activity in plasma and leucocytes
- Historical serum creatinine values
- Vital signs (blood pressure, pulse, temperature and respiration rate)
- Body weight and height
- Physical examination
- Concomitant medications , including review of pain medication and premedication
- Clinical laboratory
 - Hematology
 - Biochemistry
 - Serum Creatinine and Cystatin C
 - Urinalysis by dipstick
 - Spot urine test for proteinuria
 - HbsAg, HCV, HIV
 - Serum pregnancy test (beta HCG)
 - Vit D
 - PT, PTT
 - C3, C4
 - Urine Lyso Gb3 concentration
 - Plasma Lyso Gb3
 - Plasma Gb3
- Electrocardiogram
- Chest X-ray – an X-ray from the previous three months is acceptable
- Cardiac function assessment with echocardiography and stress test
- Review of inclusion and exclusion criteria
- Request subject approval

Schedule the patient for the next visit.

9.1.2 Visits A and B (2 and 1 Month \pm 7 days before Visit 1)

The following procedures will be performed:

- Clinical laboratory
 - Serum Creatinine and Cystatin C
 - Spot urine test for proteinuria
- Concomitant medications including review of pain medication and premedication
- Adverse event assessment

Final enrolment approval will be determined after Visit B.

Schedule the patient for the next visit.

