10. ANALYSIS OF EFFICACY ENDPOINTS

10.1. Estimated Glomerular Filtration Rate (eGFR_{CKD-EPI})

The change in eGFR will be examined by comparing the change in annualized slope of eGFR while on Replagal[®] (“Pre-switch”) to the slope in eGFR after switch to pegunigalsidase alfa treatment (“Post-switch”). Due to the nature of the prevalence of this rare disease and the variability of disease state between patients, using patients as their own control provides a rational method for clinical and statistical analysis of this patient population.

10.1.1. eGFR Estimation

eGFR will be calculated based on the value of the serum creatinine values according to the CKD-EPI formula:

$$\text{eGFR (mL/min/1.73 m}^2\text{)} = 141 \times \min(\text{Scr}/\kappa, 1)^\alpha \times \max(\text{Scr}/\kappa, 1)^{-1.209} \times 0.993^{\text{Age}} \times 1.018 \text{ [if female]} \times 1.159 \text{ [if black / African American]}$$

where Scr is serum creatinine (mg/dL), κ is 0.7 for females and 0.9 for males, α is -0.329 for females and -0.411 for males, min indicates the minimum of Scr/ κ or 1, and max indicates the maximum of Scr/ κ or 1. (Note to programmer: serum creatinine can be found in two categories (CHEMISTRY and ENZYMATE) in the SDTM. Both will be used to estimate eGFR)

The age should be the actual age when the subject’s serum creatinine is collected, the calendar age at each timepoint should be used in the formula to be consistent with that in the Electronic Data Capture (EDC) system.

The eGFR will not be calculated again if its value is available from the CRF system (all eGFR values are calculated for the screening assessments).

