10.3. Plasma Gb3 / Lyso-Gb3 and Urine Lyso-Gb3 Concentrations

Descriptive statistics of plasma Lyso-Gb3 concentration (nM) will be summarized at each visit. The change and percent change from baseline will be summarized as well. The summaries will be presented for the three subgroups in Section 7.4.

The plasma Lyso-Gb3 levels at all visits and the corresponding change and percent change from baseline will be presented in a per subject table. The plasma Lyso-Gb3 levels over time will be presented graphically by a spaghetti plot, for all individual subjects, and for by gender.

In addition, the number and percentage of patients with a reduction from baseline with thresholds of 20%, 30%, 40% and 50% will be summarized at each visit.

Descriptive statistics of plasma Gb3 concentration (nM) will be summarized at each visit and the change and percent change from baseline will be summarized for overall and by the three subgroups in Section 7.4. The change and percent change from baseline will also be presented in the data listing as well.

Descriptive statistics of urine Lyso-Gb3 concentration (pM/mM Creatinine) will be summarized at each visit for overall and the three subgroups in Section 7.4. The change and percent change from baseline will be summarized as well.

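### Plasma Lyso-Gb3 reduction counts after the switch have no on-agalsidase reference for change or variability, although Screening and Visit 1 samples could supply one

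*SAP*

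**What the plan says.** The protocol (6.1) gives the purpose of the run-in: "Patients will enter the study for 3 month Screening period for baseline data generation". SAP 4 confirms the treatment during it: "Patients will be screened and evaluated over 3 months while continuing on agalsidase alfa".

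The visit schedule (Protocol 9, 9.1.1 and 9.1.3; SAP 4.2) places plasma Lyso-Gb3, plasma Gb3 and urine Lyso-Gb3 at Screening, Visit 1 and Visits 7, 14, 20 and 27. The interim screening Visits A and B do not include them.

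SAP 7.3 defines the baseline: "The baseline for this study is defined as the assessment made at Visit 1 prior to the first infusion of pegunigalsidase alfa". An earlier value enters only as a substitute: "If not available, the last assessment before receiving the first treatment of pegunigalsidase alfa will be used as baseline".

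SAP 10.3 summarises the three biomarkers by visit, with change and percent change from that baseline. For plasma Lyso-Gb3 it adds a per-subject table, a spaghetti plot and a threshold table (14.2.2.1.3), in which "the number and percentage of patients with a reduction from baseline with thresholds of 20%, 30%, 40% and 50% will be summarized at each visit". It names no Screening-to-Visit 1 change, no threshold count for the run-in and no count of increases.

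For eGFR, SAP 10.1 does use pre-switch data as a comparator, on the ground that "using patients as their own control provides a rational method for clinical and statistical analysis of this patient population".

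**The concern.** The study has no control arm, and its patients have already had at least 2 years of agalsidase alfa. A fall from one Visit 1 value may reflect the switch, assay and day-to-day variation, or a trend already under way. A count of patients below a threshold cannot separate these, and because it looks in one direction only it is above zero even when nothing has changed.

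The design supplies a reference. Screening to Visit 1 (3 months) and Visit 1 to Visit 7 (six 2-week intervals, 12 weeks) are nearly equal in length and come from the same patients, one without the switch and one with it. The Screening and Visit 1 pairs would also estimate within-patient variability, for which the documents give no figure. Without that reference, a reader of the threshold table cannot tell how many of the counted patients would have been expected had treatment not changed.

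**Working it through.** There is no figure in the plan to reproduce: SAP 4.1 says no formal sample size calculation was done, and neither document gives a within-patient variance for these biomarkers. The following is an illustration.

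**Inputs.** n = 22 (SAP 4.1); thresholds r = 20, 30, 40 and 50% (SAP 10.3). Assumed: no true change, independent log-normal within-patient errors, CV from 10 to 30%.

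**Formula.** s² = ln(1 + CV²). The log ratio of a post-switch value to baseline has variance k·s², with k = 2 for a single baseline value and k = 1.5 for the mean of two (on the log scale). Then

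P(apparent reduction ≥ r) = 1 − Φ( −ln(1 − r) / (s√k) ).

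**Worked case, CV 20%, r = 20%.** s = √ln(1.04) = 0.198; −ln(0.8) = 0.223.
- Single baseline: 0.223 / (0.198 × √2) = 0.797, giving 21.3%, or 4.7 of 22.
- Mean of two: 0.223 / (0.198 × √1.5) = 0.920, giving 17.9%, or 3.9 of 22.

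**Share of unchanged patients crossing each threshold at one visit**

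| Assumed CV | ≥20%, Visit 1 baseline (of 22) | ≥30% | ≥40% | ≥50% | ≥20%, mean of two |
|---|---|---|---|---|---|
| 10% | 5.7% (1.2) | 0.6% | <0.1% | <0.1% | 3.4% |
| 15% | 14.5% (3.2) | 4.5% | 0.8% | <0.1% | 11.1% |
| 20% | 21.3% (4.7) | 10.1% | 3.4% | 0.7% | 17.9% |
| 25% | 26.1% (5.7) | 15.3% | 7.1% | 2.3% | 23.0% |
| 30% | 29.5% (6.5) | 19.5% | 10.9% | 4.8% | 26.7% |

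The problem lies mainly at 20 and 30%. At 50%, noise accounts for at most about 1 of 22 over this range.

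**Averaged baseline.** The within-patient SE of change falls by 1 − √(1.5/2) = 13.4%, a modest gain.

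**Why not subtract the run-in change patient by patient?** Write e0, e1 and e2 for the errors at Screening, Visit 1 and Visit 7. The difference of changes is (e2 − e1) − (e1 − e0) = e2 − 2e1 + e0, with variance 6s² against 2s² for the simple change, so its SE is √3 ≈ 1.7 times as large. It also reuses the Visit 1 error. Its covariance with e2 − e1 is 3s², so the correlation is 3/√12 = 0.866. Under no true change the probability that both are negative is 1/4 + arcsin(0.866)/(2π) = 5/12. Given a chance fall at Visit 7 (probability 1/2), that fall therefore exceeds the run-in change 5 times in 6. A rule crediting the switch whenever the fall exceeds the run-in change would mostly pass the noise it was meant to screen out.

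Taken separately, the two intervals are comparable: with no true change, the Screening-to-Visit 1 and Visit 1-to-Visit 7 log ratios have the same distribution, with variance 2s². Setting the two group distributions side by side is therefore informative, provided it stays descriptive.

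**The case against.** The case for leaving the plan alone has real content, and much of it stands.

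- A reader might infer that post-switch values have no on-agalsidase reference at all. That is not so. Visit 1 is taken before the first study infusion and after continued agalsidase alfa, so it is an on-agalsidase level. What is missing is a reference for change and variability.
- A reader might infer that the SAP never compares before with after. For eGFR it does: SAP 10.1.3 compares pre- and post-switch slopes by paired t-test with a 95% confidence interval.
- A reader might see a contradiction with Protocol 6.1. The stated purpose of the run-in is at least partly met by the screening-period creatinine values that enter the pre-switch eGFR slope, and the protocol promises no run-in contrast for biomarkers.
- A reader might conclude that the Screening values go unused. The by-visit summaries, the per-subject table and the spaghetti plot may show them; SAP 10.3 neither names nor excludes Screening, and the table shells are in a separate document. Even so, a displayed value is not a summarised run-in change or a threshold count.
- A reader might extend the thresholds to all three biomarkers, or accumulate the noise across visits. The thresholds are for plasma Lyso-Gb3 only and are tabulated visit by visit, so only the per-visit figures apply.
- The threshold table supplements change and percent change with mean, SD and range, so increases are visible elsewhere. Eligibility does not select on Lyso-Gb3, so noise alone does not push the mean log change downward. This limits the concern about noise to the threshold counts, but it does not address a trend already present on agalsidase alfa.

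**Conclusion.** The point holds in a limited form. For the three substrate biomarkers the SAP plans no Screening-to-Visit 1 change, and the plasma Lyso-Gb3 reduction counts have neither a run-in counterpart nor a count of increases. With no true change, about 6 to 30% of patients (1 to 6-7 of 22) would be counted at the 20% threshold at any one visit, falling to about 0 to 5% at the 50% threshold. These figures rest on an assumed CV of 10 to 30% and on independent log-normal errors; neither comes from the documents, and the trial's own run-in pairs would replace the assumption.

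It does not follow that the biomarker results are invalid or that a Visit 1 baseline is wrong. That baseline is prespecified and unambiguous, safety is the primary objective, and the biomarker analyses carry no test or success criterion. The change is worth making because it is cheap and gives the reader the missing measure of noise.

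**What to change.** Amend SAP 10.3, keeping everything descriptive:

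1. For plasma Lyso-Gb3, plasma Gb3 and urine Lyso-Gb3, add the Screening-to-Visit 1 change and percent change as a column beside Visit 1 to Visit 7.
2. In the plasma Lyso-Gb3 threshold table, apply the same four thresholds to the run-in interval and show increases of the same size beside reductions, in both intervals. State how size is matched; on a ratio scale a 20% reduction (0.8) mirrors a 25% increase (1/0.8), and a 50% reduction mirrors a doubling.
3. Add a sensitivity summary of change from the mean of Screening and Visit 1. The Visit 1 baseline in SAP 7.3 can remain the main definition.

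Compare the run-in and post-switch distributions at group level. Do not add a paired difference of the two changes, or a rule that credits the switch only where a fall exceeds the run-in change, since both reuse the Visit 1 error. Because SAP 7.5 records an interim analysis already done, label these summaries as added after it.

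The cost is SAP wording and a few table columns, with no new samples or visits. The reduction percentages may look less favourable beside the run-in column.
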